23.4. Criteria for Suspending/Terminating a Study Site

Boston Scientific Corporation reserves the right to stop the inclusion of subjects at a study site at any time after the study initiation visit if no subjects have been enrolled for a period beyond 3 months after site initiation, or if the site has multiple or severe protocol violations/noncompliance without justification and/or fails to follow remedial actions.

In the event of termination of site participation, all study devices and testing equipment, as applicable, will be returned to BSC unless this action would jeopardize the rights, safety or well-being of the subjects. The IRB/EC and regulatory authorities, as applicable, will be notified. All subjects enrolled in the study at the site will continue to be followed for 12

Study Reference Number: S2382 Confidential

Form/Template 90702637 Rev/Ver AH STOPPER China Protocol, 92040370 Rev/Ver AD Page 50 of 59

months. The Principal Investigator at the site must make provision for these follow-up visits unless BSC notifies the investigational site otherwise.

According to Section 20, all study participants who have received study device treatment will need continuous adverse events assessment and report. The principal investigators at study sites need to continue the follow-up unless being notified by Boston Scientific.

24. Publication Policy

BSC requires disclosure of its involvement as a sponsor or financial supporter in any publication or presentation relating to a BSC study or its results. BSC will submit study results for publication (regardless of study outcome) following the conclusion or termination of the study. Boston Scientific Corporation adheres to the Contributorship Criteria set forth in the Uniform Requirements of the International Committee of Medical Journal Editors (ICMJE; http://www.icmje.org). In order to ensure the public disclosure of study results in a timely manner, while maintaining an unbiased presentation of study outcomes, BSC personnel may assist authors and investigators in publication preparation provided the following guidelines are followed.

- All authorship and contributorship requirements as described above must be followed.
- BSC involvement in the publication preparation and the BSC Publication Policy should be discussed with the Coordinating Principal Investigator(s) and/or Executive/Steering Committee at the onset of the project.
- The First and Senior authors are the primary drivers of decisions regarding publication content, review, approval, and submission.

25. Reimbursement and Compensation for Subjects

25.1. Subject Reimbursement

Travel and other expenses incurred by subjects as a result of participation in the study will be reimbursed in accordance with pertinent country laws and regulations and per the study site's regulations.

27. Abbreviations and Definitions

See Table 27.1 for Abbreviations.

Table 27.1 Terms and Abbreviations

Table 27.1 Terms and Abbreviations		
AE	Adverse Event	
ALT	Alanine aminotransferase, Serum glutamic pyruvic transaminase (SGPT)	
AST	Asparagine aminotransferase, Serum glutamic oxaloacetic transaminase	
	(SGOT)	
AVM	Arteriovenous malformation	
BCLC	Barcelona Clinical Liver Cancer staging	
CBC	Complete Blood Count	
CR	Complete Response	
CRO	Contract Research Organization	
cTACE	Conventional transarterial chemoembolization	
CRF	Case Report Form	
DEB-TACE	Drug eluting bead-transarterial chemoembolization	
DSMB	Data Safety Monitoring Board	
EC	Ethics Committee	
ECG	Electrocardiogram	
ECOG	Eastern Cooperative Oncology Group	
eCRF	Electronic Case Report Form	
EDC	Electronic Data Capture	
GCP	Good Clinical Practices	
HBV	Hepatitis B virus	
HCC	Hepatocellular Carcinoma	
HCV	Hepatitis C virus	
ICH-GCP	International Conference on Harmonization-Good Clinical Practices	
IDE	Investigational Device Exemption	
INR	International normalized ratio	
IRB	Institutional Review Board	
IRRP	Independent Response Review Panel	
ISO	International Standards	
ITT	Intent-to-Treat	
mRECIST	Modified RECIST	
MRI	Magnetic Resonance Imaging	
PD	Progressive Disease	
PR	Partial Response	
SAE	Serious Adverse Event	
SD	Stable Disease	
TACE	Transarterial chemoembolization	
TTP	Time to Disease Progression	
UADE	Unanticipated Adverse Device Effect	

[figure not shown]
See Tables 27.2 for Definitions

Table 27.2: Definitions

Term	Definition
BCLC Staging System	The Barcelona Clinic Liver Cancer Staging System is a well-accepted system that uses tumor stage, liver function, physical status, and cancer related symptoms, to classify the stages with a treatment algorithm. ⁴
Child-Pugh Score	The Child-Pugh score is a measure of liver function. ⁴ It is calculated from the sum of the points for each Child Pugh Classification (CPC) criteria. See Appendix B
ECOG Performance Status	An Eastern Cooperative Oncology Group (ECOG) assessment of performance status describes a patient's level of functioning in terms of their ability to care for them self, daily activity, and physical ability (walking, working, etc.). See Appendix A.
Investigational Device	Boston Scientific Corporation ONCOZENE™ or TANDEM™ Microspheres loaded with doxorubicin
mRECIST Criteria	A post-treatment assessment of tumor response by magnetic resonance imaging (MRI) scan. See Appendix C.
Near-Stasis	A degree of stasis where near complete loss of intra-tumoral vascularity is shown by a slowed contrast flow for 2-5 heartbeats.
Source Data	All information in original records of clinical findings, observations, or other activities in a clinical investigation, necessary for the reconstruction and evaluation of the clinical investigation.
Target Tumor	The lesion can be measured in at least one dimension ≥ 1 cm; The lesion appears to be suitable for accurate and repeat measurement; The lesion shows intratumoral arterial enhancement

Attachment A: Diagnostic criteria included in the management guideline issued by China's Ministry of Health in 2017

- 1. Subject diagnosed as hepatitis B or C, or liver cirrhosis of any cause should receive ultrasound and AFP test at least every 6 months. The clinical diagnosis of HCC can be made if the intrahepatic nodule of ≤2cm in diameter is identified and at least two of the following four tests indicate the typical "fast in and fast out" HCC characteristics with significant enhancement of lesion in the arterial phase and reduced enhancement of portal vein or delayed phase: dynamic enhancement MRI, dynamic enhancement CT, contrast-enhanced ultrasonography and Primovist dynamic enhancement MRI. For intrahepatic nodule of >2cm in diameter, the clinical diagnosis of HCC can be made if one of the four tests indicate the typical HCC characteristics.
- 2. Subject diagnosed as hepatitis B or C, or liver cirrhosis of any cause: HCC diagnosis can be confirmed with liver biopsy or close imaging follow-up if the intrahepatic nodule is ≤ 2cm in diameter and only one of the above four imaging tests indicate typical HCC characteristics; For intrahepatic nodule >2cm in diameter and no typical HCC characteristics by any of the four tests, the diagnosis should be confirmed by liver biopsy.

Appendix B: ECOG Performance Status

Performance Status Criteria: ECOG and Karnofsky Performance Scores

Score	Description
0	Fully active, able to carry on all pre-disease performance without restriction
1	Restricted in physically strenuous activity but ambulatory and able to carry out work of a light or sedentary nature (e.g. light housework, office work).
2	Ambulatory and capable of all self-care but unable to carry out any work activities. Up and about more than 50% of waking hours.
3	Capable of only limited self-care, confined to bed or chair more than 50% of waking hours.
4	Completely disabled. Cannot carry on any self-care. Totally confined to bed or chair.
5	Dead

Appendix C: Child-Pugh Score

		1 point	2 points	3 points
Serum	mg/dL	<2	2-3	>3
Bilirubin	μmol/L	<34.2	34.2-51.3	>51.3
Serum	g/dL	>3.5	2.8-3.5	<2.8
Albumin	g/L	>35	28-35	<28
INR		<1.7	1.7-2.30	>2.30
Ascites		None	Mild	Severe
Hepatic encephalopathy		None	Grade I-II	Grade III-IV

Class A: 5-6 points, Class B: 7-9 points, Class C: 10-15 points

Appendix D: mRECIST Response Assessment of Target Lesion for HCC

Target Lesions	
Response Category	mRECIST
CR	Disappearance of any intratumoral arterial enhancement in all target
	lesions
PR	At least a 30% decrease in the sum of the diameters of viable
	(enhancement in the arterial phase) target lesions, taking as reference
	the baseline sum of the diameters of target lesions.
SD	Any cases that do not qualify for either PR or PD
PD	An increase of at least 20% in the sum of the diameters of viable
	(enhancing) target lesions, taking as a reference the smallest sum of
	the diameters of viable (enhancing) target lesions recorded since
	treatment started.

Study Reference Number: S2382 Confidential

Form/Template 90702637 Rev/Ver AH STOPPER China Protocol, 92040370 Rev/Ver AD Page 59 of 59

Appendix E: EASL Response Assessment of target lesion for HCC

Response Category	EASL Criteria		
Complete Response (CR)	Disappearance of all known disease and no new lesions		
	determined by two observations not less than 4 weeks apart		
Partial Response (PR)	At least 50% reduction in total tumor load of all measurable		
	lesions determined by two observations not less than 4		
	weeks apart		
Stable Disease (SD)	Any cases that do not qualify for either PR or PD		
Disease Progression (PD)	At least 25% increase in size of one or more measurable		
	lesions or the appearance of new lesions

1 PROTOCOL SYNOPSIS

1 480 5 61			
A Single-arm Trial of Transcatheter Arterial Chemoembolization with Tandem Microspheres in the Treatment of Localized Hepatocellular Carcinoma			
Study Objective	The primary objective of this study is to evaluate the safety and efficacy of transcatheter arterial chemoembolization with Tandem Microspheres loaded with Epirubicin in the treatment of subjects with localized hepatocellular carcinoma (HCC)		
Study Device	Tandem Microspheres are spherical, tightly calibrated, biocompatible, non-resorbable, hydrogel microspheres coated with Polyzene®-F, an inorganic polymer.		
Planned Indication(s)	Tandem Microspheres are indicated	d for the	
for Use	embolization of arteriovenous malf	formations and	
	hypervascular tumors		
Device Specifications	Tandem Microspheres are stored in 2 ml and 3 ml sized syringes. They are available in a range of sizes (40, 75, and 100 µm). Microspheres used will be at the discretion of the treating physician(s) based on the tumor size and/or vascular structure.		
	Microspheres Diameter (μ])	Size (ml)	
	40	2	
	40	3	
	75	2	
	75	3	
	100	2	
	100	3	
Study Design	This is a prospective, single-arm, multicenter study to evaluate the safety and efficacy of transcatheter arterial chemoembolization with Tandem Microspheres loaded with Epirubicin in the treatment of subjects with localized hepatocellular carcinoma. All qualified subjects will be enrolled in the study and receive transcatheter arterial chemoembolization treatment with Tandem Microspheres loaded with Epirubicin		
Sample Size	109 subjects (including 10% loss to follow-up)		
Number of Study Sites	10 clinical centers will be participating in the study		
Primary Effectiveness Endpoint	The primary effectiveness endpoint for this clinical trial is 6-month objective tumor response rate (ORR).		

Secondary Endpoints	ORR at 30-day and 3-month
	• Time to Progression (TTP)
	Time to Extrahepatic Spread
	Proportion Progression-Free (PPF) at one year
	Overall survival at one year
	The frequency of Tandem treatment associated adverse
	events
Study Enrollment	Subject will be qualified to be enrolled in the clinical trial once signed the IRB/EC approved informed consent, meet all inclusion criteria and does not meet any of the exclusion criteria. All enrolled subjects will receive the transcatheter arterial chemoembolization with Tandem Microspheres. Enrollment timepoint will be based on subject receiving transcatheter arterial chemoembolization treatment with Tandem Microspheres loaded with Epirubicin
Follow-up Plan	Follow-up will be conducted at 30 days and 3, 6, and 12 months post initial treatment. The tests during the follow-ups include:
	 Laboratory (include Complete Blood Count, blood biochemistry, blood coagulation function, renal and liver function, electrolyte, AFP) and imaging tests (include plain scan plus enhanced MRI, Chest plain scan CT) at 30 days and 3, 6 and 12 months post procedure ECG at 3 months post procedure
Study Duration	The study will end when all subjects completed the 12-month follow-up post initial treatment, or withdraw (death loss to follow-up, or withdraw consent).

	Page / O	
Inclusion Criteria	Subjects may be included in the study only if they meet all of the following criteria:	
	1. Subject is able to provide informed consent and must sign the Institutional Review Board/Ethics Committee (IRB/EC) approved Informed Consent Form.	
	2. Male or female of age \geq 18 and \leq 75 years.	
	 Confirmed diagnosis of HCC according to the diagnostic criteria included in the management guideline issued by China's Ministry of Health in 2017. 	
	4. HCC is diagnosed for the first time or recurrence of tumor after surgical or ablation treatment.	
	5. Single tumor less than 7cm in diameter or multiple tumors with maximum 3 lesions with >1cm in diameter, individual diameter <7cm and less than 10cm in total diameter.	
	6. no previous chemotherapy, radiotherapy or transarterial embolization (with or without chemotherapy) for HCC	

7. Preserved liver function (Child-Pugh A or B7).

8. ECOG Performance Status 0 or 1.

Exclusion Criteria	Subjects will be excluded for the following reasons:	
	 Presence of vascular invasion or extra-hepatic spread of disease, or diffuse HCC, defined as >50% liver involvement, or arteriovenuous fistula Macrovascular invasion of main or primary branches of portal vein at entry into the study 	
	3. Any contraindication for TACE treatment	
	4. Any contraindication for Epirubicin administration	
	 5. Advanced liver disease (bilirubin levels >2 mg/dl, AST or ALT >5 times upper limit of normal) 6. Renal failure or insufficient renal function 	
	7. Subject unable to receive MRI examination	
	8. Pregnant or breast feeding woman, or plan to become pregnant during treatment or within 12 months of treatment	
	9. Couldn't commit reliable birth control measures during treatment or within 12 months of treatment.	
	10. Subject is participating other investigational drug or device clinical trial within 30 days of signing the informed consent.	
	11. Subject is not suitable to participate in the study as judged by investigator	
Statistical Methods		
Primary Study Hypotheses	The primary hypothesis is that the 6-month ORR in the Tandem microspheres embolization and drug delivery arm is higher than the performance goal (PG).	
	The null (H ₀) and alternative (H ₁) hypotheses for this primary endpoint are presented below.	
	H_0 : $P_e \leqslant PG$	
	$H_1: P_e > PG$	
	where P _e is the expected 6-month ORR (%).	
Statistical Test	A normal approximation test will be used to assess the one-sided hypotheses of the test device superior to the PG	

Success Criteria for the PG	The test device will be concluded to be superior to the PG in the primary analysis if the one-sided lower 97.5% confidence bound for the test device performance in 6-month ORR is greater than PG.
Sample Size Parameters	The overall sample size (N=109) is driven by the primary effectiveness endpoint. • Power ≥ 85% • One-sided significance level = 2.5% (alpha) • PG for 6-month ORR = 45% • Expected 6-month ORR = 60% • Total N=98 subjects are required for 6-month assessment • Attrition rate = 10% (loss to follow-up in 6 months) • Approximately N=109 subjects to enroll

2 INTRODUCTION

This Statistical Analysis Plan (SAP) has been designed to document the planned analyses to be consistent with the objectives of the STOPPER China protocol. The specified analyses may be provided in reports to competent authorities and/or for scientific presentations and/or manuscripts. The primary analyses will be based on the 6-month assessment for the tumor objective response rate (ORR) after the treatment initiation (i.e. the 1st treatment). The study success will be based on the primary effectiveness testing hypotheses (i.e. the only statistical hypotheses).

3 PRIMARY ENDPOINTS ANALYSES

The sample size is justified by hypotheses parameters and driven by the 6-month primary effectiveness endpoint to preserve adequate statistical testing power.

The primary effectiveness hypothesis is planned for being tested after the initial treatment and through 6 months at the pre-specified significance level of one-sided 2.5%.

3.1 Primary Effectiveness Endpoint

The 6-month ORR is selected to be assessed for the primary effectiveness endpoint. The goal is designed to demonstrate that Tandem meets the PG in terms of the ORR through 6 months post treatment initiation.

3.1.1 Definition of the ORR

Objective tumor response will be assessed by two response evaluation systems for solid tumors:

- European Association for the Study of the Liver (EASL); and
- Modified Response Evaluation Criteria in Solid Tumors (mRECIST).

The EASL and mRECIST responses measure on MRI in HCC subjects treated with chemoembolization to predict long-term survival. The mRECIST response demonstrated higher survival correlation than the EASL (cf. Prajapati et al, 2013 Annuals of Oncology).

EASL Response Assessment of Target Lesion for HCC:

Response Category	EASL Criteria
Complete Response (CR)	Disappearance of all known disease and no new lesions determined by two observations not less than 4 weeks apart
Partial Response (PR)	At least 50% reduction in total tumor load of all measurable lesions determined by two observations not less than 4 weeks apart
Stable Disease (SD)	Any cases that do not qualify for either PR or PD
Disease Progression (PD)	At least 25% increase in size of one or more measurable lesions or the appearance of new lesions

mRECIST Response Assessment of Target Lesion for HCC:

Response Category	mRECIST Criteria
Complete Response (CR)	Disappearance of any intratumoral arterial enhancement in all target lesions
Partial Response (PR)	At least a 30% decrease in the sum of the diameters of viable (enhancement in the arterial phase) target lesions, taking as reference the baseline sum of the diameters of target lesions.
Stable Disease (SD)	Any cases that do not qualify for either PR or PD
Disease Progression (PD)	An increase of at least 20% in the sum of the diameters of viable (enhancing) target lesions, taking as a reference the smallest sum of the diameters of viable (enhancing) target lesions recorded since treatment started.

A responder is for a subject being assessed as CR or PR as opposed to a non-responder is for being assessed as SD or PD (i.e. numerator). Subjects with valid assessment (i.e. CR, PR, SD, or PD) will be considered as evaluable subjects (i.e. denominator).

A subject without 6 month tumor assessment after the treatment initiation (i.e. the 1st DEB-TACE) will be regarded as a missing data and will be excluded from the primary effectiveness endpoint analysis.

3.1.2 Effectiveness Hypotheses

The primary effectiveness hypothesis to be tested is that the 6-month ORR in subjects treated with Tandem meets the PG at a one-sided significance level of 2.5%.

The null hypothesis (H_0) states that the PG is not met as opposed to the alternative hypothesis (H_1) which states that the PG is met. The hypotheses inequalities are shown below:

 H_0 : $Pt \le PG$ (not met)

 H_1 : Pt > PG (met)

where Pt is the 6-month ORR for the subjects treated with Tandem and the PG is 45%. The PG development is based on the PRECISION V, an international multicenter phase II randomized clinical trial (RCT).

3.1.3 Effectiveness Sample Size

The overall sample size is driven by the primary effectiveness endpoint. Approximately 109 subjects are planned to be enrolled in the single-arm study. The sample size justification is based on the following assumptions.

- Power > 85%
- One-sided significance level (alpha) = 2.5%
- PG for 6-month ORR = 45%

- Expected 6-month ORR = 60%
- A minimum of 98 evaluable subjects to be required at 6 months
- Attrition rate in 6 months $\leq 10\%$
- A maximum of 109 subjects to be enrolled in the study at baseline

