3.1.6 Additional Justification of Sample Size Parameters

The PG of 6-month ORR for Tandem was based on the primary endpoint results (6-month tumor response by EASL) in the PRECISION V (Lammer et. al. 2010), a phase II RCT, published by CardioVascular and Interventional Radiology (Springer).

[figure not shown]

Fig. 2 Tumor response at 6 months (LOCF) (MITT population and advanced patient group* ***). * More advanced disease was at least one of Child-Pugh B, ECOG 1, undergone prior curative treatment (i.e., recurrent disease), and presence of bilobar disease. In accordance with the EASL criteria: complete response (CR)—complete disappearance of all known viable tumor (assessed via uptake of contrast in the arterial phase of the MRI scan) and no new lesions; partial response (PR)—50% reduction in viable tumor area of all

measurable lesions; stable disease (SD)—all other cases; progressive disease (PD)—25% increase in size of one or more measurable lesions or the appearance of new lesions. Objective response (OR) was defined as CR + PR, and disease control (DC) as CR + PR + SD. ** Analysis of advanced patient subgroup: OR rate, P=0.038; DC rate, P=0.026; CR rate, P=0.091 (chi-square analysis)

The 6-month ORRs were reported as 51.6% (48/93) vs. 43.5% (47/108) for DC Bead and cTACE respectively. The 95% exact confidence intervals were estimated by SAS: 51.6% with 95% CI: 41.0%, 62.1% and 43.5% with 95% CI: 34.0%, 53.4% for DC Bead and cTACE

respectively. Therefore in order to demonstrate the significant treatment effect over the cTACE, the PG of 45% based on the performance of cTACE was chosen.

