5.10.4 EASL Criteria

The EASL response assessment of target lesion for HCC is to measure on MRI in HCC subjects treated with chemoembolization to predict long-term survival. The EASL criteria describes below:

Response Category	EASL Criteria
Complete Response (CR)	Disappearance of all known disease and no new lesions determined by two observations not less than 4 weeks apart
Partial Response (PR)	At least 50% reduction in total tumor load of all measurable lesions determined by two observations not less than 4 weeks apart
Stable Disease (SD)	Any cases that do not qualify for either PR or PD

Disease Progression (PD)	At least 25% increase in size of one or more measurable lesions
	or the appearance of new lesions
	of the appearance of new resions

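### The EASL table for the primary endpoint scores total tumor, while the EASL definition behind the 45% performance goal scores viable tumor, so the two rates are not shown to measure the same thing

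*SAP*

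**What the plan says.** Protocol 12.1.1.1 puts the primary hypothesis on EASL response. The EASL table has the same content in SAP 3.1.1, SAP 5.10.4 and Protocol Appendix E:

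- A subject counts as PR (partial response) when this condition holds: "At least 50% reduction in total tumor load of all measurable lesions determined by two observations not less than 4 weeks apart".
- The condition for CR (complete response) is worded as "Disappearance of all known disease and no new lesions determined by two observations not less than 4 weeks apart".
- Whatever is left over, short of progression, falls to SD (stable disease).

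SAP 3.1.6 derives the 45% PG from 6-month EASL response in PRECISION V, where the cTACE arm had 47/108 = 43.5%. It reproduces that trial's definition from a figure caption. CR there is "complete disappearance of all known viable tumor (assessed via uptake of contrast in the arterial phase of the MRI scan) and no new lesions". For PR the caption asks for a halving of viable tumor area across the measurable lesions. The caption mentions no second observation.

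The mRECIST rows in SAP 3.1.1 do refer to viable tumor: "At least a 30% decrease in the sum of the diameters of viable (enhancement in the arterial phase) target lesions". The EASL rows beside them do not.

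The core laboratory reads both criteria at baseline, 30 days and 3, 6 and 12 months, and Protocol 13.3 leaves the reading rules to a Manual of Operations. SAP 3.1 states the goal as showing that "Tandem meets the PG in terms of the ORR through 6 months post treatment initiation".

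**The concern.** The trial has one arm, and its sole comparator is the PG. The test is interpretable only if the observed rate and the PG count the same kind of response.

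The choice of tumor measure matters especially after embolization. Protocol 19.1 describes ischemic necrosis as a consequence of the procedure, so a treated lesion can lose its enhancement while keeping its size. A rule based on viable tumor counts that as response; a rule based on total tumor does not. Under the single label EASL, the SAP carries one rule for the test and another for the benchmark, and neither document bridges them. If the table were followed literally, a miss could reflect the measuring rule rather than the device.

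**Working it through.** **1. The plan's own figures.** Inputs (SAP 3.1.3): PG 0.45, expected rate 0.60, one-sided alpha 2.5%, power 85%, attrition 10%.

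n = [(1.960·√(0.45·0.55) + 1.036·√(0.60·0.40)) / 0.15]² = 97.7, so 98. Normal-approximation power at 98 is 85.1%, and 98/0.9 = 108.9, so 109. The source rates also reproduce: 48/93 = 51.6% and 47/108 = 43.5%. The sample-size arithmetic is sound; the issue is what is counted.

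**2. The two definitions side by side.**

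| | Trial table (SAP 3.1.1, 5.10.4; Appendix E) | Definition behind the PG (SAP 3.1.6) |
|---|---|---|
| CR | All disease gone, no new lesions | No arterially enhancing tumor left, no new lesions |
| PR | Total load down at least 50% | Viable area down 50% |
| Second observation | Required, at least 4 weeks later | Not mentioned |
| PD | 25% growth of a measurable lesion, or a new lesion | Same |

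**3. A worked lesion.** Assume a round 5 cm lesion, fully enhancing at baseline. After treatment it still measures 5 cm.

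| | mRECIST | PG definition | Trial EASL table, read literally |
|---|---|---|---|
| Enhancing part falls to 3.5 cm | 3.5/5 = 0.70, down 30%: PR | Area 1 − 0.7² = 0.51, down 51%: PR | Total load unchanged: SD |
| Enhancement disappears | CR | CR | SD |

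**4. Direction.** If a lesion is fully enhancing at baseline, viable load equals total load at the start and cannot exceed it later. Halving total load then also at least halves viable load, so every literal responder is a responder on the PG definition, but not the reverse. Under that assumption the literal reading can only lower the ORR. Without it the direction is open. Inclusion criterion 4 admits recurrence after ablation, and if a lesion has a non-enhancing part at baseline, that part could shrink while the viable part does not.

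**5. Confirmation.** Visit windows (SAP 5.8.1) are days 16–44, 77–105, 169–197 and 351–379. Gaps between scheduled scans:

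- 30 days to 3 months: 77 − 44 = 33 to 105 − 16 = 89 days
- 3 to 6 months: 169 − 105 = 64 to 197 − 77 = 120 days
- 6 to 12 months: 351 − 197 = 154 to 379 − 169 = 210 days

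Every gap exceeds 28 days, so an earlier response can be confirmed at an existing visit. For a response first seen at 6 months, the next scheduled scan is at 12 months, and the plan does not say whether that scan counts.

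**6. Scale only, on assumed losses.** Suppose the 60% expectation is on the viable-tumor scale and the literal table loses 5%, 10% or 20% of responders. The measurable rate becomes 57%, 54% or 48%, and normal-approximation power at n = 98 becomes 67%, 43% or 9%. If the 60% already reflects the trial's table, nothing is lost and power stays at 85%. The documents support neither supposition, so this is not an estimate.

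**The case against.** The strongest reply is that the table is incomplete shorthand. The criterion is named EASL, and the SAP's only gloss on that name (3.1.6) describes viable, enhancing tumor. The tables are headed as applying to target lesions, and Protocol 11.4 requires a target lesion to show arterial enhancement. One core laboratory reads all images to a manual that may well specify viable tumor. This stands as far as practice goes: a reader might infer that the laboratory is measuring total size, and the documents do not show that. It does not cure the text. Enhancement is a rule for selecting lesions, not for measuring response, and the mRECIST rows show that viability was written down where it was meant.

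Three further inferences are tempting and not supported:

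- **That the source did not confirm responses.** A caption's silence does not show this, and the publication is not available here.
- **That a response first seen at 6 months is a non-responder by default.** The confirmation rule has no upper time limit, the core laboratory reads at 12 months, and no text bars that scan from confirming. Such cases are also probably few, because Protocol 8.2 lists absence of mRECIST partial response after two treatments within 6 months among the events that end study treatment.
- **That power falls below 85% by a stated amount.** Any loss of responders is assumed, and the 60% expectation is tied to neither definition.

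**Conclusion.** The point holds on the tumor measure. The written rule for the only hypothesis test differs from the rule behind its PG, and the difference changes how a necrotic but unshrunken lesion is classified. That is a wrong stated rule, not merely a missing detail. It should be fixed before the primary analysis.

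Its size is unknown. The documents do not say how many subjects would be reclassified or what the core laboratory does in practice. Only under full enhancement at baseline does the literal reading move the ORR in a known direction, downward. A reader might go further and say that type I error is certainly unaffected, or certainly inflated; the documents support neither as a general statement.

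Confirmation is a secondary point: the plan needs to say which scans may confirm. The 52-versus-54 responder cut-off, the source's LOCF/MITT basis and the precedence of EASL over mRECIST are separate issues and are not relied on here.

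**What to change.** Before the primary analysis:

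1. Amend SAP 3.1.1 and 5.10.4 and Protocol Appendix E so that the core laboratory scores EASL CR and PR on viable, arterially enhancing tumor, as in SAP 3.1.6. Check that the Manual of Operations agrees.
2. Keep the written confirmation requirement for the primary analysis unless the source publication shows that it used none. State which scans may confirm, including whether the 12-month scan may confirm a 6-month response.
3. Report 6-month response under the other confirmation rule as a sensitivity analysis.
4. Report response under the present total-load wording as a sensitivity analysis, where the measurements exist.

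Cost: SAP text, and an Appendix E amendment with the approvals that Protocol section 14 requires. No new scans are needed, but stored images may need re-reading if total load was measured. The downside should be stated openly. Scoring viable tumor makes success easier than the literal text does, as would dropping confirmation, which is why the as-written reading has to be reported alongside. If the source's confirmation rule cannot be established, comparability on that element stays unresolved.
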